2.3.8.1.5. Spleen and Response Assessment by Investigator

Spleen and response assessment will be performed locally by investigators based on radiological images and using the modified myeloproliferative neoplasms research and treatment (IWG-MRT) response criteria (Table 1, Table 2). In addition, tumor assessment of progressive disease (PD) can also be done based on clinical evidence other than radiological images, which is collected on the CRF.

2.3.8.1.6. Spleen Assessment by IRC

Data collected based on radiological images assessed by the IRC will be evaluated and summarized.

2.3.8.1.7. Best Overall Response

The best overall response is the best response in order of CR/PR/CI/RWCI/SD/PD/NE recorded from the start of the treatment until disease progression or the start of subsequent antineoplastic therapy.

2.3.8.2. Primary Efficacy Endpoints

2.3.8.2.1. Definition and Primary Analysis

The primary endpoints are the spleen response rate based on MRI at Week 24 (spleen volume reduction, SVR at Week 24) and symptom response rate at Week 24 (symptom improvement at Week 24). The SVR at Week 24 is defined as the proportion of subjects who achieve $\geq 35\%$ reduction in spleen volume at Week 24 and symptom improvement at Week 24 is defined as the proportion of subjects who have $\geq 50\%$ reduction in total symptom score at Week 24.

The primary analysis of SVR at Week 24 will be based on assessment of MRI by the IRC. The SVR at Week 24 based on assessment of MRI by the investigators will be evaluated and used as supportive evidence.

2.3.8.2.2. Analysis Methods

No treatment comparison between treatment arms for SVR at Week 24 will be performed. The estimates of the SVR at week 24 and symptom improvement at Week 24 in each treatment arm will be presented along with 95% exact confidence intervals based on the treated analysis set.

2.3.8.3. Secondary Efficacy Variables

2.3.8.3.1. Response-Related Endpoints per modified IWG-MRT criteria

Overall Response Rate

Overall response rate (ORR) is defined as the proportion of subjects who achieve complete remission (CR) or partial remission (PR) per modified IWG-MRT criteria based on the overall response assessment for the treated population.

Clinical Improvement

Clinical improvement rate (CI) is defined as the proportion of subjects who achieve CI per modified IWG-MRT criteria based on the overall response assessment for the treated population. Clinical response rate (CRR) is defined as the proportion of subjects who achieve CR, PR, or CI per modified IWG-MRT criteria for the treated population.

Anemia, Spleen, and Symptom Response per Modified IWG-MRT Criteria

Anemia response, spleen response, and symptom response are all defined per modified 2013 IWG-MRT criteria as [Table 1](#).

Analysis Methods

An estimate of the ORR/CRR rate in each treatment arm will be presented along with 95% exact confidence intervals. The number and percentage of subjects falling into each response category will be descriptively tabulated.

CI rate, rate of anemia response, spleen response, and symptom response will be analyzed using the same method as it is done for ORR/CRR.

Best overall response will be tabulated.

The ORR/CRR and other response endpoints such as CI, anemia response, spleen response, symptom response per modified IWG-MRT criteria based on assessment of IRC and investigator will be evaluated and analyzed separately.

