1.1.5.1.1. Spleen and Anemia Response

Spleen and anemia responses were assessed according to the 2013 IWG-MRT criteria. Eight (34.8%) of 23 subjects with baseline splenomegaly had a spleen response (5 of 14 subjects in Arm A and 3 of 9 subjects in Arm B) defined as \geq 50% spleen size reduction by palpation lasting at least 12 weeks. Four (4) of 13 (30.8%) subjects who were transfusion dependent at baseline (3 of 8 subjects in Arm A and 1 of 5 subjects in Arm B) became transfusion independent during the study. Among 7 subjects who had CR or PR, 4 subjects with splenomegaly at baseline also achieved splenic response, and 3 subjects who were transfusion dependent at baseline became transfusion independent. Additional analysis of spleen response, defined as \geq 50% spleen size reduction by palpation at 24 weeks from treatment initiation, were performed and 9 (39.1%) of 23 evaluable subjects (6 subjects in Arm A and 3 subjects in Arm B) had a response.

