4.1. Inclusion Criteria

Each potential subject must satisfy all of the following criteria to be enrolled in the study.

- 1. \geq 18 years of age
- 2. Diagnosis of PMF according to the revised WHO criteria (Attachment 6); or PET-MF or PPV-MF according to the IWG-MRT criteria (Attachment 7). A report from the local laboratory for diagnosis of MF must be reviewed and approved by the sponsor.
- 3. DIPSS intermediate-2 or high risk MF (Attachment 8)
- 4. Measurable splenomegaly prior to study entry as demonstrated by:
 - palpable spleen measuring ≥5 cm below the left costal margin. The edge of the spleen should be measured in centimeters from the mid-clavicular line on the left side of the abdomen to the point of greatest splenic protrusion.

OR

- spleen volume of ≥ 450 cm³ measured by magnetic resonance imaging (MRI)
- 5. Active symptoms of MF as demonstrated by a symptom score of at least 5 points (on a 0 to 10 scale) on at least one of the symptoms or a score of 3 or greater on at least 2 of the following symptoms: night sweats, itchiness, abdominal discomfort, pain under ribs on left side, early satiety, bone or muscle pain, and inactivity.
- 6. Criterion modified per Amendment 1.
- 6.1 Documented progressive disease during or after JAK inhibitor therapy defined as worsening of splenomegaly-related abdominal pain at any time after the start of JAK inhibitor therapy, and

EITHER

- no reduction in spleen volume or size after 12 weeks of JAK inhibitor therapy
 OR
- worsening splenomegaly at any time after the start of JAK inhibitor therapy documented by:
 - increase in spleen volume from nadir by 25% measured by MRI or computed tomography (CT), or
 - increase in spleen size by palpation, CT, or ultrasound
 - o for splenomegaly of 5-10 cm at the start of JAK inhibitor treatment, at least 100% increase in palpable spleen size from nadir is required;

- o for splenomegaly of >10 cm at the start of JAK inhibitor treatment, at least 50% increase in palpable spleen size from nadir is required;
- o new splenomegaly must measure at least 5 cm.
- 7. ECOG performance status 0, 1 or 2 (Attachment 9)
- 8. Criterion modified per Amendment 1.
- 8.1 Hematology laboratory test values within the following limits:
 - Absolute neutrophil count (ANC) ≥1.5 x 10^9 /L (ie, ≥1,500/mm³) independent of growth factor support
 - Platelets $\geq 75 \times 10^9 / L$ (ie, $\geq 75,000 / mm^3$) independent of platelet transfusion support
- 9. Criterion modified per Amendment 1.

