2.3.8.1.4. Response Assessment Criteria

All assessments will be done according to the modified myeloproliferative neoplasms research and treatment (IWG-MRT) response criteria defined in the protocol ([Table 1](#), [Table 2](#)).

Table 1: Response Categories

Response Category	Required Criteria
	For all response categories, benefit must last for ≥ 12 weeks to qualify as a response
Clinical Improvement (CI)	The achievement of anemia, spleen or symptoms response without progressive disease or increase in severity of anemia, thrombocytopenia, or neutropenia ^a
Anemia Response	Subjects not transfusion dependent at baseline: a ≥ 20 g/dL increase in Hb ^b Transfusion dependent subjects at baseline: becoming transfusion independent. Transfusion independence is defined as absence of any pRBC transfusions for at least 12 “rolling” weeks ^b
Spleen Response	A baseline splenomegaly that is palpable at 5-10 cm, below the LCM, becomes not palpable or A baseline splenomegaly that is palpable at >10 cm, below the LCM, decreases by $\geq 50\%$ A spleen response requires confirmation by MRI showing $\geq 35\%$ spleen volume reduction
Symptoms Response	A $\geq 50\%$ reduction in the modified MFSAF v2.0 TSS ^c
Progressive Disease	Splenomegaly requires MRI showing a $\geq 25\%$ increase in spleen volume from baseline or Appearance of a new splenomegaly that is palpable at least 5 cm below the LCM or A $\geq 100\%$ increase in palpable distance, below LCM, for baseline splenomegaly of 5-10 cm or A 50% increase in palpable distance, below LCM, for baseline splenomegaly of >10 cm or Leukemic transformation confirmed by a bone marrow blast count of $\geq 20\%$ or A peripheral blood blast content of $\geq 20\%$ associated with an absolute blast count of $\geq 1 \times 10^9/L$ that lasts for at least 2 weeks
Stable Disease	Belonging to none of the above listed response categories
Relapse	No longer meeting criteria for at least CI after achieving CR, PR, or CI, or Loss of anemia response persisting for at least 1 month or Loss of spleen response persisting for at least 1 month

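### Modified IWG-MRT spleen response appears to be reported over all treated subjects, although anyone who entered on MRI volume without a spleen palpable at 5 cm or more cannot meet it; a second row for subjects able to respond is needed

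*SAP*

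**What the plan says.** **Entry.** Protocol 4.1, criterion 4, asks for measurable splenomegaly shown in one of two ways joined by OR: "palpable spleen measuring ≥5 cm below the left costal margin", or a volume of at least 450 cm³ "measured by magnetic resonance imaging (MRI"). The MRI route sets no palpation minimum.

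**Endpoint.** SAP Table 1 (section 2.3.8.1.4) gives two routes to spleen response, and protocol Table 9 agrees. The first is "A baseline splenomegaly that is palpable at 5-10 cm, below the LCM, becomes not palpable". The second is "A baseline splenomegaly that is palpable at >10 cm, below the LCM, decreases by" at least 50%. MRI is an added condition, not a third route: "A spleen response requires confirmation by MRI showing" a reduction of at least 35%.

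**Analysis.** SAP 2.3.8.3.1 defines ORR, CI and CRR for the treated population and gives ORR and CRR a 95% exact confidence interval per arm. It then says: "CI rate, rate of anemia response, spleen response, and symptom response will be analyzed using the same method as it is done for ORR/CRR". SAP 2.1.4.1 defines the Treated set as everyone with at least one dose and makes it the primary efficacy set. Protocol 11.4 plans a proportion with a 95% confidence interval for these endpoints and names no restricted denominator.

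**The concern.** A subject can be eligible, be treated and lose a large share of spleen volume, yet still be counted as a spleen-response failure because the baseline spleen was palpable at less than 5 cm or not at all. If such subjects sit in the denominator, the reported rate mixes two things: how often the drug produces the response, and how many subjects were in a position to show it. The reader cannot separate them from the planned table. No analysis set in SAP 2.1.4 helps. The Week 12/24 set requires an observed measurement, not a palpable baseline spleen. The optional evaluable-population sensitivity analysis in protocol 11.4 supports the co-primary endpoints only and is not defined.

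Anemia response raises a related question. Protocol Table 9 limits the hemoglobin route to subjects with baseline Hb below 10 g/dL, so subjects at or above 10 g/dL who are not transfusion dependent could not respond. SAP Table 1 has no such limit.

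**Working it through.** **1. Can a subject enter without a spleen palpable at 5 cm or more?** Yes. Criterion 4 permits it through MRI volume. Criterion 6.1 does not close the route: besides worsening splenomegaly-related pain, it accepts no reduction in spleen volume or size after 12 weeks of JAK inhibitor therapy, or a 25% volume increase from nadir on MRI or CT.

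**2. Can that subject meet the spleen response?** No. Both routes in SAP Table 1 start from a palpable baseline length of 5-10 cm or more than 10 cm. What counts is the baseline value, the last one on or before first dose (SAP 2.1.1), so a few subjects could change category after screening.

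**3. Dilution.** Let p be the rate among subjects able to respond and f the share of treated subjects not able to. Then

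all-treated rate = (1 − f) × p.

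This is never above p, and it equals p only when f = 0 or p = 0. The documents give neither f nor p, so both are assumptions here. With p = 35%:

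| f (assumed) | Subjects, if all 107 enrolled were treated | All-treated rate |
|---|---|---|
| 0% | 0 | 35.0% |
| 5% | about 5 | 0.95 × 35 = 33.3% |
| 10% | about 11 | 0.90 × 35 = 31.5% |
| 20% | about 21 | 0.80 × 35 = 28.0% |

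The 107 is from SAP 1.4.

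**4. The only stated rate for a spleen response of this kind.** Protocol 1.1.5.1.1, on the earlier imetelstat study: "Eight (34.8%) of 23 subjects with baseline splenomegaly had a spleen response". 8/23 = 34.8% reproduces (exact 95% CI 16.4% to 57.3%). Over all 33 subjects of that study it would be 8/33 = 24.2% (11.1% to 42.3%). This shows the mechanism only and does not estimate f in the present trial.

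**5. Other endpoints.** The co-primary spleen endpoint (SAP 2.3.8.2.1) is a volume reduction of at least 35% by MRI at Week 24, so MRI-route subjects can respond. PR in SAP Table 2 accepts a 35% volume reduction or a non-palpable spleen, so it is not closed to them. CI loses only its spleen route.

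**6. Anemia response, side by side.**

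| | Protocol Table 9 | SAP Table 1 |
|---|---|---|
| Subjects not transfusion dependent | Baseline Hb <10 g/dL | No baseline Hb condition |
| Required increase | ≥2 g/dL | ≥20 g/dL |

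The SAP's own footnote on worsening anemia uses 20 g/L, which equals 2 g/dL, so the table entry may be a unit slip. The baseline condition matters: under the DIPSS table (protocol Attachment 8), a subject with Hb of 10 g/dL or more can still score 4 points (age 1, leukocytes 1, blasts 1, symptoms 1), which is intermediate-2 and eligible.

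**The case against.** **The denominator is inferred.** SAP 2.3.8.3.1 attaches the treated population to ORR, CI and CRR but not to anemia, spleen or symptom response, and the same-method sentence follows one about exact intervals. This is fair. Still, the Treated set is the primary efficacy set, no text restricts it, and no other denominator is offered. Naming it is part of the fix.

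**The treated-set rate is not wrong.** As a proportion of everyone dosed it is valid and conservative. This stands. The dilution is relative to subjects able to respond.

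**The effect is small against sampling error.** With about 54 per arm (assumption: 107 split evenly), 19/54 = 35.2% has an exact 95% CI of 22.7% to 49.4%. A shift of 2 to 7 points lies well inside it. The endpoint is secondary, and SAP 2.3.8.1.1 plans no comparison between arms. This also stands and keeps the point minor. A systematic shift is not part of what the interval describes, however, and it is cheap to show.

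**Two stronger readings are tempting.** A reader might take 34.8% against 24.2% as the size of the effect here. The documents do not support that: 10 of the 33 earlier subjects had no palpable spleen (protocol 1.1.5), whereas this trial requires measurable splenomegaly. A reader might also infer that the planned rate spoils a comparison with the earlier study. No section plans that comparison; the historical comparison in SAP 1.3 concerns the co-primary endpoints. The definitions differ too: the earlier study used a palpation reduction of at least 50% lasting 12 weeks, while here a 5-10 cm spleen must become non-palpable and MRI must confirm. Matching denominators would not make the rates comparable.

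**Conclusion.** The point holds as a minor improvement. On the natural reading of SAP 2.3.8.3.1, subjects whose baseline spleen is not palpable at 5 cm or more are automatic non-responders for the secondary spleen response, and the reported rate is scaled by (1 − f). The direction is certain if any such subject was treated. The size is unknown: 1.7 to 7 points off a 35% rate for f between 5% and 20%, both figures being assumptions, and nothing at f = 0. It would go too far to say that the rate reflects the entry route rather than response, since over this range at least 80% of the underlying rate is retained.

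For anemia response, the conclusion is limited to the mismatch between SAP Table 1 and protocol Table 9. Whether some subjects are excluded by definition depends on which text governs.

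**What to change.** In SAP 2.3.8.3.1:

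- State that the denominator for spleen response is the Treated set.
- Add a row reporting spleen response, with n and exact 95% CI per arm, among subjects with a baseline spleen palpable at 5 cm or more. Keep the treated-set row beside it.
- Reconcile SAP Table 1 with protocol Table 9 on the baseline hemoglobin condition and the required increase (including its unit). Then report anemia response also among subjects eligible under the reconciled definition, again beside the treated-set row.

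Baseline palpation, hemoglobin and transfusion status are already collected, so the cost is two table rows. The downside is smaller denominators and wider intervals in those rows. For example, if 11 of 54 subjects in an arm could not respond and 15 did (assumed counts), the treated-set row is 15/54 = 27.8% (exact 95% CI 16.5% to 41.6%) and the added row is 15/43 = 34.9% (21.0% to 50.9%). Specifying both rows in advance also removes a later choice of denominator.

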2.3.8.3.2. Duration of Response

Definition

Response endpoints include: CR/PR, CR/PR/CI, anemia response, spleen response, and symptom response per modified IWG-MRT criteria. For each of the response endpoints, duration of response will be calculated from the date of initial documentation of a response to the date of first documented evidence of PD or death, whichever occurs first, regardless of the use of subsequent anti-cancer therapy prior to PD or death. Subjects who are progression-free and alive, or have unknown status will be censored at the last disease assessment.

Analysis Methods

The Kaplan-Meier method will be used to descriptively summarize each duration of responses for responders: CR/PR, CR/PR/CI, Spleen, Anemia, and Symptom Response

per modified 2013 IWG-MRT criteria. Analyses based on IRC response and investigator response will be performed separately.

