1.1.5.1.3. Subject Status and Time on Treatment

The median duration of treatment was 8.6 months (range 1.4 to 21.7 months) for all 33 subjects in Arms A and B. The median duration of treatment was 15.5 months (range 6.5 to 21.7 months) for the subjects with CR, PR, or CI, 15.5 months (range 14.0 to 21.7 months) for subjects with CR or PR, and 6.9 months (range 1.4 to 19.3 months) for subjects with stable disease. Subjects who did not have CR, PR, CI, or evidence and maintenance of clinical benefit (defined as \geq 50% improvement in leukocytosis, a \geq 50% improvement in thrombocytosis, a \geq 50% decrease in palpable splenomegaly, or a \geq 50% improvement in RBC transfusion requirement) were discontinued from treatment even if they did not meet criteria for progression. Of the 33 subjects, 25 (75.8%) discontinued treatment, 16 (48.5%) of whom discontinued due to insufficient response or the start of alternative therapy. Two (2) subjects progressed and 1 subject relapsed while on treatment. Two (2) subjects (6.1%) discontinued due to an adverse event. As of the cut-off date (December 2014) for this analysis, 8 subjects are still on treatment, 6 of them with ongoing CR, PR, or CI.

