9.2.2. Endpoints

Primary Endpoints

The co-primary endpoints of this study are spleen response rate and symptom response rate. Spleen response rate is defined as the proportion of subjects who achieve $\geq 35\%$ reduction in spleen volume at Week 24 from baseline as measured by imaging scans. Symptom response rate is defined as the proportion of subjects who have $\geq 50\%$ reduction in TSS at Week 24 from baseline as measured by the modified MFSAF v2.0 diary.

Secondary Endpoints

- CR or PR per modified 2013 IWG-MRT criteria
- CI per modified 2013 IWG-MRT criteria
- Spleen response, symptoms response, and anemia response per modified 2013 IWG-MRT criteria

- Duration of spleen response, duration of symptoms response, duration of CR or PR, duration of CI, and duration of anemia response
- OS
- Patient reported outcomes including EORTC QLQ-C30, EQ-5D-5L, BPI, and PGIC
- Safety profile of imetelstat
- PK profile of imetelstat

Exploratory Endpoints

- TA, TL and hTERT at baseline and the change from baseline
- Cytogenetic response and molecular response
- Leukemia free survival

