- The distributions of duration of spleen response and duration of symptom response will be summarized using Kaplan-Meier estimates based on responding subjects. The estimated median will also be reported along with a 95% confidence interval. Duration of CR or PR, CI, and anemia response will be provided descriptively using similar methods based on responding subjects.
- The distribution of OS will be summarized using similar Kaplan-Meier methods.
- Change in spleen volume, change in TSS, and change in PRO endpoints from baseline will be descriptively summarized over time.
- Additional analyses to be performed for the subjects who were initially treated with 4.7 mg/kg and subsequently dose escalated to 9.4 mg/kg per the guidance outlined in Section 6.

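### The protocol names duration of clinical improvement as its own secondary endpoint, but the SAP plans only CR/PR and pooled CR/PR/CI durations and gives no reason

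*SAP*

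**What the plan says.** Protocol 9.2.2 lists among the secondary endpoints: "Duration of spleen response, duration of symptoms response, duration of CR or PR, duration of CI, and duration of anemia response". Protocol 11.4 repeats the separation in the analysis plan: "Duration of CR or PR, CI, and anemia response will be provided descriptively using similar methods based on responding subjects".

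SAP 2.3.8.3.2 gives a different list. Its definition reads: "Response endpoints include: CR/PR, CR/PR/CI, anemia response, spleen response, and symptom response per modified IWG-MRT criteria". Its analysis method applies Kaplan-Meier summaries to "each duration of responses for responders: CR/PR, CR/PR/CI, Spleen, Anemia, and Symptom Response". Every duration runs from first documentation of the response "to the date of first documented evidence of PD or death, whichever occurs first".

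For response rates, SAP 2.3.8.3.1 keeps CI as its own category: "Clinical improvement rate (CI) is defined as the proportion of subjects who achieve CI per modified IWG-MRT criteria". It then defines a separate clinical response rate that pools CR, PR and CI.

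**The concern.** The group for the protocol's endpoint is subjects with CI. The group in the SAP is subjects with CR, PR or CI. If remissions and clinical improvements last for different times, the pooled curve describes neither. A reader who looks for the protocol's duration of CI would find only the pooled figure and might take it for the durability of clinical improvement. The SAP neither flags nor explains the change.

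**Working it through.** The point is mainly a comparison of texts. The plan states no figure to reproduce.

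**Step 1. Set the lists side by side.**

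| Duration of | Protocol 9.2.2 and 11.4 | SAP 2.3.8.3.2, definition | SAP 2.3.8.3.2, method |
|---|---|---|---|
| CR or PR | yes | yes | yes |
| CI | yes | no | no |
| CR, PR or CI pooled | no | yes | yes |
| Spleen response | yes | yes | yes |
| Symptom response | yes | yes | yes |
| Anemia response | yes | yes | yes |

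The SAP makes the same substitution in both places, so a slip in one line is unlikely. No other SAP section plans a duration for CI alone.

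**Step 2. Could CI mean CI or better?** For rates, SAP 2.3.8.3.1 reports CI and the CR/PR/CI pool as two quantities. SAP 2.3.8.1.7 ranks CI below CR and PR. The SAP therefore treats CI as a separate category, and only for duration is the pool left without a CI counterpart.

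**Step 3. Do the component durations supply it?** Under SAP Table 1, CI is an anemia, spleen or symptoms response together with no progressive disease and no worsening of anemia, thrombocytopenia or neutropenia. A component responder can fail the cytopenia condition, and can also be a CR or PR subject. The component groups overlap the CI group but are not the same group.

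**Step 4. What the earlier imetelstat study shows (protocol 1.1.5.1 and 1.1.5.1.3).** The 12 responders were 7 CR/PR and 5 CI. Median time on treatment was 15.5 months for all 12 (range 6.5 to 21.7). For the remissions it was "15.5 months (range 14.0 to 21.7 months) for subjects with CR or PR".

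- The CR/PR minimum is 14.0 months, so the 6.5-month value and any other below 14.0 belong to CI subjects.
- Suppose all 5 CI subjects were below 14.0 months. The 6th of the 12 ordered values would then be the CR/PR minimum, 14.0. The 7th would be the second-lowest CR/PR value, at most the CR/PR median of 15.5. The pooled median would be at most (14.0 + 15.5)/2 = 14.75 months. The reported value is 15.5, so at least one CI subject was at 14.0 months or more (reading the medians as ordinary sample medians).
- The CI median itself cannot be recovered from these figures.

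**Step 5. How large a distortion could be (assumptions, not trial data).** Treat the pool as two disjoint groups with exponential durations: a share w of remissions with median 14 months, and the rest CI with median m. The pooled survival is S(t) = w × 0.5^(t/14) + (1 − w) × 0.5^(t/m), and the pooled median solves S(t) = 0.5.

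| w | m (months) | Pooled median (months) | Excess over m |
|---|---|---|---|
| 0.10 | 4 | 4.40 | 10% |
| 0.10 | 9 | 9.38 | 4% |
| 7/12 = 0.58 | 4 | 7.91 | 98% |
| 7/12 = 0.58 | 9 | 11.57 | 29% |
| any | 14 | 14.0 | 0% |

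The excess is small when remissions are rare and zero when the medians agree.

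**The case against.** The strongest defence is that CI acts as a floor. The response tables define relapse as falling below at least CI after CR, PR or CI, so a CR/PR/CI duration could be read as the duration of at least CI. The protocol does not define the CI group either; it speaks only of responding subjects. This has some force, but the SAP's separate CI rate counts against it, and SAP 2.3.8.3.2 does not use relapse as its end event.

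Three stronger readings are tempting, and the documents support none of them.

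- **That the durability of clinical improvement is never examined.** The SAP gives a Kaplan-Meier duration for each of the three component responses. What is missing is CI as an endpoint. Moreover, because every SAP duration ends at progression or death, a CI curve under that rule would not measure time to loss of CI.
- **That the protocol requires the group whose best response is CI.** It does not say so. Best response is known only after follow-up, so selecting on it conditions on a future outcome. It drops subjects who reached CI and later deepened to PR or CR, which would tend to shorten the estimate.
- **That the earlier study shows remissions carrying the pooled median.** Its figures are time on treatment, not response duration. They place the shortest times in CI subjects but do not show a shorter CI median.

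The appearance of CR/PR subjects in two of the summaries is no defect in itself: these are overlapping descriptive summaries with no test attached.

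**Conclusion.** The mismatch is real and explicit. If the SAP is followed as written, a secondary endpoint named in the protocol is not reported, and no reason is recorded. Priority is low: the endpoint is descriptive, the co-primary analyses are untouched, and the component durations cover part of the ground.

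This conclusion rests on the two lists and on the SAP's own use of CI as a separate category, not on any assumed difference in durations. The numerical effect in this trial is unknown. The 4% to 98% excess holds only under the stated assumptions (CI median 4 to 9 months, remission share 10% to 58%) and should not be quoted as an estimate for this trial.

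**What to change.** In SAP 2.3.8.3.2:

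- Add a descriptive Kaplan-Meier summary per arm of duration of CI, for the subjects counted in the CI rate of SAP 2.3.8.3.1 and measured from first documentation of CI. State that subjects who later reach PR or CR stay in the group.
- Label any version restricted to best response CI as supplementary, because it conditions on later outcome.
- Keep CR/PR/CI as a supplementary pooled summary.
- State that, under the SAP's end event, these curves show time to progression or death, not time to loss of CI.

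The cost is one more descriptive summary per arm, produced for both assessments if the SAP's split between independent review and investigator is applied. The downside is wide intervals if few subjects have CI.
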